#### I.2.d.3. SAFETY MEASURES

**The Concise Health Risk Tracking (CHRT)** (Trivedi et al, 2011): The Concise Health Risk Tracking (CHRT) is a validated clinician-rated scale evaluating three independent factors (current suicidal thoughts and plans, perceived lack of social support, and hopelessness). It has excellent psychometric properties and can be used to monitor suicidal risk in clinical practice and research settings. The time scale for the CHRT is the last three days.

#### I.2.e. RELIABILITY TRAINING

All site study staff chosen to be involved in the assessment of study subjects are very familiar with standardized clinician-rated measures such as the SCID-5, the HAM-D6, the MADRS and the CHRT. They have all received extensive training in the use of these instruments through videotaped and live interviews of mock patients.

#### I.2.f. PATIENT ADHERENCE TO PROTOCOL

Every effort will be made to encourage patients to comply with the procedures and the assessments involved in study. Patients will be compensated for their time at each visit, at a rate determined appropriate by the IRB (estimated compensation: \$20.00/hour). We believe that this level of subject compensation, while non-coercive, facilitates adherence to assessments and procedures that require frequent, inconvenient visits. Subjects and clinicians will be asked to guess which arm of the study the subjects were in at the end of the study to assess if blinding was successful.

### I.3. DISCONTINUED SUBJECTS

Sites will follow the procedures in Section I.1.o. for discontinued patients.

### I.4. EVALUATION OF ADVERSE EVENTS (AEs)

#### I.4.a. DEFINITION OF AEs

##### Adverse Event

An adverse event is any untoward medical occurrence in a clinical study subject administered a medicinal (investigational or non-investigational) product. An adverse event does not necessarily have a causal relationship with the treatment. An adverse event can therefore be any unfavorable and unintended sign (including an abnormal finding), symptom, or disease temporally associated with the use of a medicinal (investigational or non-investigational) product, whether or not related to that medicinal (investigational or non-investigational) product. (Definition per International Conference on Harmonization [ICH]).

This definition includes any occurrence that is new in onset or aggravated in severity or frequency from the baseline condition, or abnormal results of diagnostic procedures, including laboratory test abnormalities.

#### I.4.b. REPORTING OF AEs

Observed and spontaneously reported adverse events will be recorded at each visit. Spontaneously-reported adverse events will be classified as mild, moderate or severe. Patients shall be allowed to contact the investigator or a member of his staff at any time between visits concerning adverse events or worsening of symptoms.

All adverse events and special reporting situations, whether serious or non-serious, will be reported from the time a signed and dated Informed Consent Form (ICF) is obtained until completion of the subject's last study-related procedure (which may include contact for follow-up of safety). Serious adverse events, including those spontaneously reported to the site-investigator from the time a signed and dated ICF is obtained until within 30 days after the last dose of study drug must be reported using the Serious Adverse Event Form. The Investigator-Sponsor will evaluate any safety information that is spontaneously reported by a site- investigator beyond the time frame specified in the protocol.

All events that meet the definition of a serious adverse event will be reported as serious adverse events, regardless of whether they are protocol-specific assessments.

All adverse events, regardless of seriousness, severity, or presumed relationship to study drug, must be recorded using medical terminology in the source document and the Electronic Case Report Form (eCRF). Whenever possible, diagnoses should be given when signs and symptoms can be ascribed to a common medical etiology with reasonable certainty as per site clinician (e.g., cough, runny nose, sneezing, sore throat, and head congestion should be reported as "upper respiratory infection" when such a determination is made with reasonable certainty as per site clinician). Investigators must record in the eCRF their opinion concerning the relationship of the adverse event to study therapy.

All measures required for adverse event management must be recorded in the source document and reported according to Investigator-Sponsor instructions.

The Investigator-Sponsor assumes responsibility for appropriate reporting of adverse events to the regulatory authorities. The Investigator-Sponsor will also report to site investigators all serious adverse events that are unlisted (unexpected) and associated with the use of the study drug. The site investigator will report these events to the appropriate IRB.

#### I.4.b.1. TIME PERIOD FOR COLLECTION OF ADVERSE EVENTS

Adverse events and SAEs will be collected from the time of signature of informed consent throughout the treatment period and including the observation period. Unsolicited SAEs will be collected for 30 days post last study treatment.

#### I.4.b.2. FOLLOW-UP OF UNRESOLVED ADVERSE EVENTS

Any AEs that are unresolved at the patient's last AE assessment in the study are followed up by the investigator for as long as medically indicated, but without further recording in the eCRF. MGH CTNI or its designee retains the right to request additional information for any patient with ongoing AE(s)/SAE(s) at the end of the study, if judged necessary.

#### I.4.b.3. VARIABLES

The following variables will be collected for each AE:

- AE (verbatim)
- The date and time when the AE started and stopped
- Maximum intensity or intensity or changes in intensity
- Whether the AE is serious or not
- Investigator causality rating against study drug (yes or no)
- Action taken with regard to IP
- AE caused patient's withdrawal from the study (yes or no)
- Outcome

In addition, the following variables will be collected for SAEs:

- Date AE met criteria for SAE
- Date investigator became aware of SAE
- AE is serious due to [insert reason]
- Date of hospitalization
- Date of discharge
- Probable cause of death
- Date of death
- Autopsy performed
- Causality assessment in relation to study procedure(s)
- Causality assessment in relation to study drug
- Causality assessment in relation to other medication
- Description of AE

Intensities will be reported for each AE in the following categories: a) Mild (awareness of sign or symptom, but easily tolerated); b) Moderate (discomfort sufficient to cause interference with normal activities); c) Severe (incapacitating, with inability to perform normal activities).

It is important to distinguish between serious and severe AEs. Severity is a measure of intensity whereas seriousness is defined by the criteria in Section H.4.d. An AE of severe intensity need not necessarily be considered serious. For example, nausea that persists for several hours may be considered severe nausea, but not an SAE. On the other hand, a stroke that results in only a limited degree of disability may be considered a mild stroke, but would be an SAE.

Worsening symptoms of the primary study condition (i.e., MDD) should not be recorded as an AE. However, worsening of MDD will be reported as an adverse event if, in the opinion of the investigator, clinically significant worsening of depression occurs following intranasal ketamine administration. In addition, hospitalization resulting from worsening psychiatric symptoms should be recorded as an SAE in the eCRF.

Should an overdose of study drug occur, it must be reported in accordance with the procedures described below. An overdose associated with symptoms must be reported as an AE, while an overdose without associated symptoms, must be reported only on the separate MGH CTNI Clinical Study Overdose Report Form. Any overdose will also be considered a protocol violation and reported as such.

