### I.2.C. OUTCOME AND SAFETY MEASURES

#### I.2.c.1. OUTCOME MEASURES

Symptom improvement will be evaluated by assessing changes in the primary outcome measure, the self-rated Symptoms of Depression Questionnaire (SDQ) (Pedrelli et al, 2014). Brexpiprazole has shown in recent studies to have significant benefits in domains such as irritability, anger, anxiety, and nervousness. These domains are not captured or are only partially captured by standard scales such as HAM-D or MADRS. In a recent study of NSI-189, the SDQ slightly outperformed the MADRS in detecting a change over placebo because of the broader symptom net cast by the SDQ.

Secondary outcome measures include the HAM-D6, which has shown greater sensitivity to change and greater effect sizes compared to the longer, multidimensional versions of the HAM-D (e.g., HAM-D-17 and HAM-D-28) (Faries et al, 2000; Bech et al, 2010), the MADRS and the CGI-S and CGI-I (Guy, 1976).

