#### I.4.f. ADVERSE EVENTS BASED ON SIGNS AND SYMPTOMS

All AEs spontaneously reported by the patient in response to the open question from the study personnel: "Have you had any health problems since the previous visit?" or revealed by observation will be collected and recorded in the eCRF. In the collection of AEs, the recording of diagnoses is preferred (when possible) over the recording of a list of signs and symptoms. However, if a diagnosis

is known and there are other signs or symptoms that are not generally part of the diagnosis, the diagnosis and each sign or symptom will be recorded separately.

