#### I.4.h. DISEASE PROGRESSION OR WORSENING DEPRESSION

Disease progression can be considered as a worsening of a patient's condition attributable to the disease for which the study drug is being studied. It may be an increase in the severity of the disease under study and/or increases in the symptoms of the disease. The development of worsening depression should be considered as disease progression and not an AE. Events, which are unequivocally due to disease progression, should not be reported as an AE during the study. However, if worsening of depression occurs during ketamine treatment, in the opinion of the investigator, is to be reported as an adverse event.

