#### K.1.b. SAFETY

Ketamine was well tolerated after single-dose administration up to 60.0 mg, multiple-dose administration up to 35.0 mg, and single-dose administration up to 25.0 mg. There were no deaths or SAEs reported in any published study. One (1) subject was discontinued due to a treatment-related AE of mild ventricular tachycardia in one study, and no subjects were discontinued due to AEs in two other studies. The most common AEs considered by the investigator to be related to ketamine (occurring >1 incidence) were: headache (6 events), diarrhea (4 events), nausea (3 events), and anxiety (2 events), dyspepsia (5 events), pruritus generalized (3 events), headache (2 events), diarrhea (2 events), and abdominal pain (2 events). In these three studies, there were no clinically significant values, changes, or trends in clinical laboratory data. No clinically significant changes were observed in the hypothalamic-pituitary-adrenal axis hormones of cortisol, prolactin, and luteinizing hormone. There were no clinically significant changes in vital signs and electrocardiograms (ECGs), including no evidence of changes in corrected QT (QTc) prolongation.

The most frequent adverse events with brexpiprazole are akathisia, headache, and weight increase. Mean changes from baseline in Abnormal Involuntary Movement Scale and Barnes Akathisia Rating Scale total scores are significantly greater with brexpiprazole 3 mg versus placebo.

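### The default exclusion of worsening MDD from AE recording, with an exception tied to ketamine and not to the randomised drug, can leave ambiguous activation symptoms out of the safety data

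*Combined protocol and SAP*

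**What the plan says.** Two sections of the combined protocol and SAP govern worsening depression.

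- **I.4.b.3 (Variables).** The default is "Worsening symptoms of the primary study condition (i.e., MDD) should not be recorded as an AE". The next sentence makes an exception if, in the investigator's opinion, "clinically significant worsening of depression occurs following intranasal ketamine administration". A further sentence adds that "hospitalization resulting from worsening psychiatric symptoms should be recorded as an SAE in the eCRF".
- **I.4.h (Disease Progression or Worsening Depression).** "The development of worsening depression should be considered as disease progression and not an AE". The section then narrows this: "Events, which are unequivocally due to disease progression, should not be reported as an AE during the study". Its exception covers worsening *during* ketamine treatment, where I.4.b.3 says *following* administration.

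Other sections bear on how much this matters.

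- **K.1.b (Safety).** "The most frequent adverse events with brexpiprazole are akathisia, headache, and weight increase". The same paragraph reports higher scores than placebo on an involuntary-movement scale and an akathisia scale at 3 mg.
- **F.2, I.2.c.2, I.2.d.3 and Table 3.** The safety measures are vital signs, AEs, the CHRT, ECG, laboratory tests and physical examination. No akathisia or movement scale is scheduled.
- **I.4.f.** AEs come from observation and one open question: "Have you had any health problems since the previous visit".
- **I.2.c.1 and I.2.d.2.** The SDQ is chosen partly because "Brexpiprazole has shown in recent studies to have significant benefits in domains such as irritability, anger, anxiety, and nervousness", and it is described as measuring depressive symptom domains.
- **Section N.** No AE analysis is described.

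**The concern.** Whether a symptom enters the AE data depends on whether the investigator attributes it to MDD. For headache that is easy. For restlessness, agitation, or new anxiety or nervousness it is not, because these can be drug activation or depressive worsening, and the plan treats anxiety and nervousness as territory for its depression outcome scale. A blinded rater can file such a symptom as MDD and still be following I.4.b.3.

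The exception does not address this. It is triggered by ketamine, which is common to both arms, and not by brexpiprazole, which is what the trial randomises. An event that does enter through it is recorded as worsening of depression and not as an activation symptom. Under I.4.e, deterioration put down to lack of effect is then classed as having no reasonable possibility of drug causation.

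At stake is Secondary Aim 5, the safety and tolerability of brexpiprazole against placebo. With no scale as a second source, an ambiguous event left out of the AE data may appear nowhere as a harm.

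**Working it through.** **1. The two rules side by side.**

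| | I.4.b.3 | I.4.h |
|---|---|---|
| Default | Worsening MDD symptoms are not AEs | Worsening depression is progression, not an AE |
| Limiter | None | Only events unequivocally due to progression |
| Ketamine exception | *Following* administration, clinically significant, no time window | *During* ketamine treatment, no severity threshold |
| Hospitalisation | SAE | Not mentioned |

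**2. Where the wordings can diverge.** The text under Table 2 gives ketamine on Days 0, 5, 8, 11, 14 and 21, and starts the 3 mg step on Day 21. Every patient has had ketamine from Day 0, so on a literal reading of I.4.b.3 any later clinically significant worsening follows ketamine. Under I.4.h, worsening after the last dose on Day 21 may no longer count as during treatment. The two readings can therefore separate on Days 22 to 28, which hold the Day 23 and Day 28 visits. That is the scheduled 3 mg period, the dose for which K.1.b reports the scale signal.

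**3. What stays recordable.** I.4.a defines an AE as anything new or aggravated from baseline. I.4.b requires recording whatever the presumed relationship to study drug. I.4.f has symptoms outside a known diagnosis recorded separately. Akathisia recognised as such is therefore an AE. Only the ambiguous presentations are exposed.

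**4. Illustration of size.** The documents give neither an akathisia incidence nor a misfiling rate. Inputs:

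- n = 26 per arm, from Section N. As a check on that figure, a two-sample t-test at effect size 0.8, 80% power and two-sided 0.05 needs 25.5, so 26 per arm, with power 0.807. The text under Table 2 says 25 per arm; this barely matters here (0.90^26 = 0.065, 0.90^25 = 0.072).
- True active incidence p = 5%, 10% or 20% (assumed); placebo 2% (assumed).
- Share misfiled as MDD m = 0, 25% or 50%, the same in both arms (assumed; the investigator is blinded under J.7.a).

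Formulas: expected recorded active cases = 26 × p × (1 − m); recorded risk difference = (p − 0.02)(1 − m); chance of no recorded active case = (1 − p(1 − m))^26.

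| p | m | Expected active | Risk difference (points) | Chance of none in active |
|---|---|---|---|---|
| 5% | 0 | 1.30 | 3.0 | 26.4% |
| 5% | 25% | 0.98 | 2.25 | 37.0% |
| 5% | 50% | 0.65 | 1.5 | 51.8% |
| 10% | 0 | 2.60 | 8.0 | 6.5% |
| 10% | 25% | 1.95 | 6.0 | 13.2% |
| 10% | 50% | 1.30 | 4.0 | 26.4% |
| 20% | 0 | 5.20 | 18.0 | 0.3% |
| 20% | 25% | 3.90 | 13.5 | 1.5% |
| 20% | 50% | 2.60 | 9.0 | 6.5% |

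Expected placebo cases are 26 × 0.02 × (1 − m) = 0.52, 0.39 and 0.26.

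**5. Which arm loses more.** At p = 10% and m = 50% the active arm loses 2.60 − 1.30 = 1.30 expected cases and placebo 0.52 − 0.26 = 0.26. Equal misfiling leaves the ratio of incidences unchanged (10/2 = 5/1), but it shrinks the absolute excess and makes an empty active-arm cell more likely.

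**6. Is a test affected?** Fisher exact power with no misfiling is already only 2.7% at 10% versus 2%, and 33% at 20% versus 2%. The loss is to the description of harm.

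**The case against.** A reader might infer that worsening is barred from the AE data, with ketamine the only way in. The text does not support that. Clinically significant worsening following ketamine is an AE with no time limit and no need to attribute it to ketamine. Psychiatric hospitalisation is an SAE, I.4.b.4 covers suicidal events, and I.4.h excludes only unequivocal progression. Nothing instructs a site to file restlessness or akathisia as MDD. I.2.c.1 explains the choice of an efficacy scale and does not define MDD for AE purposes; the inclusion criteria use DSM-5. K.1.b itself lists anxiety among ketamine-related AEs, so the plan accepts that anxiety can be an AE. Section D.2.b suggests a lower potential for akathisia than with aripiprazole, and scheduled exposure at 3 mg is only about a week. All of this stands, and it confines the point to ambiguous symptoms.

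It is also fair that the assumed incidence moves the illustration at least as much as misfiling does: with no misfiling, the chance of an empty active arm runs from 26.4% at 5% to 0.3% at 20%.

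The safeguards still leave a gap. The limiter in I.4.h is absent from I.4.b.3. Separate recording in I.4.f applies only to symptoms not generally part of the diagnosis, which is the very judgement in doubt. The exception in I.4.b.3 misses worsening that is not clinically significant.

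**Conclusion.** The point holds as a modest defect in the recording rule. Worsening MDD is excluded by default, the exception is linked to a treatment both arms receive, and its two wordings conflict in a way that can matter after Day 21. No rule or scale separates activation from depressive worsening.

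It would go too far to conclude that akathisia will be under-counted in the active arm, or that a finding of good tolerability would be an artefact. The documents show that ambiguous events can be lost, not that they will be, and the amount cannot be derived from them. Under the assumptions above (placebo 2%, equal misfiling, 26 per arm), 50% misfiling halves the recorded risk difference and moves the chance of an empty active-arm cell from 26.4% to 51.8% at 5% true incidence, from 6.5% to 26.4% at 10%, and from 0.3% to 6.5% at 20%. The consequence is confined to the Aim 5 description. The primary SDQ analysis is untouched. This is a low-severity point, worth acting on because the change is cheap.

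**What to change.** 1. Reconcile I.4.b.3 and I.4.h so that they state one default, one limiter and one exception. Which ketamine wording applies is for the sponsor to settle.
2. For data recording only, add to both sections that new or worsened restlessness, agitation, akathisia, nervousness or anxiety, or abnormal movement after the first dose of study drug is entered as an AE whatever the presumed cause. This changes no dose, visit or treatment rule and needs no new scale.
3. In Section N, pre-specify one MedDRA group of these terms and tabulate by arm the number of patients with at least one event. Show the akathisia, restlessness and movement terms separately from the anxiety terms.

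The cost is a few sentences and a few table rows. The downside is that some true depressive worsening is counted as AEs in both arms. If 20% to 40% of patients had such a background event (an assumption), that is 26 × 0.20 = 5.2 to 26 × 0.40 = 10.4 per arm, against an excess of 26 × (0.10 − 0.02) = 2.1 at the 10% illustration. A single pooled row could therefore hide a signal, which is why the two sets of terms need separate rows.

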#### I.4.b.4. SUICIDAL IDEATION AND BEHAVIOR

The documentation and proper management of suicidal ideation by sites will be documented with the use of the CHRT completed by site clinicians during all visits.

Any patient who, based on the investigator's judgment, poses an imminent risk of suicide should be discontinued from the study (see Section J.6). All efforts should be taken to minimize the risk of suicide and the investigator should carefully monitor the patient. If during the course of the study, a patient shows evidence of suicidal behavior, the patient should be evaluated immediately or referred to their attending psychiatrist or a local emergency room for further evaluation to see if they are safe to continue in the study. The site should have the ability to direct any patient that requires emergency hospitalization to an emergency room or inpatient psychiatric unit that is within a 50-mile radius of the site. In addition, the patient should be able to contact someone at the site 24 hours per day should they have serious worsening of their condition.

Suicide and attempted suicide, irrespective of the method, but occurring in connection with the use of IP, should be reported as AEs (all suicides are SAEs; attempted suicides can be either serious or non-serious adverse events). The event should be identified as suicide or attempted suicide, and the method of the suicide or attempt should be provided. If an attempted suicide meets the criteria for

an SAE, the event must be reported according to the guidelines in Section I.4.i.2. If a suicide attempt does not meet the criteria for an SAE, it should be considered a reportable event.

All events of suicidal ideation and behavior will be carefully monitored. These include events of suicide attempts, emergence or significant worsening of suicidal ideation, completed suicides, and suicidal behavior. If a suicidal behavior meets the criteria for a SAE, according to the guidelines in I.4.i.2, investigators are required to report the event according to the guidelines for SAEs described in Sections I.4.i.2

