#### I.4.e. CAUSALITY COLLECTION

The investigator will assess the causal relationship (i.e., the relationship to study treatment) between the IP and AEs, and answer "yes" or "no" to the question "Do you consider that there is a reasonable possibility that the event may have been caused by the investigational product?"

Causal relationship in cases where the disease under study has deteriorated due to lack of effect will be classified as no reasonable possibility.

For SAEs, causal relationship will also be assessed. Note that for SAEs that could be associated with any study procedure, the causal relationship is implied as "yes."

A guide to the interpretation of the causality question is found in the MOP.

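### The qualifier tying suicide and attempted suicide to use of the IP in I.4.b.4 conflicts with the general AE rules and could leave non-serious attempts inconsistently recorded as AEs

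*Combined protocol and SAP*

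**What the plan says.** I.4.b.4 (Suicidal Ideation and Behavior) states that suicide and attempted suicide, by whatever method, "but occurring in connection with the use of IP, should be reported as AEs". A parenthesis in the same sentence classes every suicide as an SAE and allows attempts to be serious or non-serious AEs. The section then adds, with no condition on the IP: "If a suicide attempt does not meet the criteria for an SAE, it should be considered a reportable event".

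The general rules are broader:

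- I.4.a, definition: "An adverse event does not necessarily have a causal relationship with the treatment".
- I.4.b, recording: "All adverse events, regardless of seriousness, severity, or presumed relationship to study drug, must be recorded".
- I.4.b.1, time period: "Adverse events and SAEs will be collected from the time of signature of informed consent throughout the treatment period".
- I.4.b.3 lists causality as one of the variables collected for each AE. I.4.e asks it as a yes/no question: "Do you consider that there is a reasonable possibility that the event may have been caused by the investigational product".

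Two further provisions bear on a suicidal event attributed to the depression itself. I.4.b.3 and I.4.h treat worsening depression as disease progression rather than an AE, except where it occurs with ketamine treatment. I.4.e says that causality in cases where the disease has "deteriorated due to lack of effect will be classified as no reasonable possibility".

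**The concern.** A site looking up how to handle a suicide attempt will go to the section written for it, and that section carries a condition that the general AE rules do not. The protocol does not say whether the condition concerns cause or timing. Nor does it say whether IP means brexpiprazole/placebo alone or also the intranasal ketamine that both arms receive. Two careful sites could therefore enter the same non-serious attempt differently.

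At stake is the safety comparison. The last secondary aim in F.2 characterizes safety against placebo using, among other things, treatment-emergent adverse events. I.4.c applies MedDRA coding and analysis to the AEs entered in the study database. An attempt that reaches the medical monitor but is never entered as an AE would not appear in that comparison. Attempts that a site attributes to undertreated depression could differ between an effective and an ineffective arm, so recording that depends on attribution is more than untidy.

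**Working it through.** The plan states no figure on this point, so the check sets the provisions side by side.

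**Step 1: the qualifier read as cause.** An attempt counts under the sentence if it is linked to the IP. I.4.a says that an AE needs no causal link, and I.4.b requires recording whatever the presumed relationship. In I.4.b.3 and I.4.e causality is a rating attached to an AE, not a test for becoming one. On this reading I.4.b.4 contradicts all of them.

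**Step 2: the qualifier read as timing.** An attempt counts if it happens while the patient is using the IP. I.4.b.1 starts collection at signature of consent, before any IP is taken. I.1.a sets a screening period of 7 to 28 days, which can include taper and washout of excluded psychotropic drugs. An attempt in that period would fall outside the sentence but inside I.4.b.1, so the conflict remains. The consequence differs, however: a pre-randomization event belongs to no arm, so its omission affects the safety record and not the comparison between arms.

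**Step 3: what other rules capture without an IP condition.**

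| Event | Other provision | Captured? |
|---|---|---|
| Completed suicide | I.4.i.1 lists death; I.4.b reports every event meeting the SAE definition as an SAE | Yes |
| Attempt meeting an SAE criterion | I.4.i.1; I.4.b; I.4.b.4 sends it to I.4.i.2 | Yes |
| Hospitalization for psychiatric worsening | I.4.b.3 records it as an SAE in the eCRF | Yes |
| Clinically significant suicidal ideation or behavior | M.7: site report within 24 business hours | Yes, for oversight |
| Suicidal thinking at visits | CHRT at all visits (Table 3) and named in the F.2 safety aim | Yes, as a scale |
| Non-serious attempt | I.4.b.4 makes it reportable; I.4.b records it if the site treats it as an AE | Not assured as an AE entry |

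**Step 4: the last row.** Being reportable is not the same as being entered as an AE. The reporting described in I.4.i.2 and M.7 goes to the IRB, the regulator, the medical monitor and the sponsor-investigator, and neither section says that the event thereby enters the AE dataset. The parenthesis in I.4.b.4 does call attempts AEs, but it sits inside the qualified sentence, so a site can read it as subject to the same condition.

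**Step 5: a second route to the same omission.** Without the qualifier, a site that attributes a non-serious attempt to the depression could still point to the disease-progression wording in I.4.b.3 and I.4.h. Both must be addressed.

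**Scale of one event.** With 26 patients per arm (section N), one attempt is 1/26 = 3.8% of an arm. One omission would take an arm from 3.8% to 0% on that event.

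**The case against.** The strongest reply is that I.4.b is categorical, covers every AE, and already requires a non-serious attempt to be recorded. I.4.b.4 nowhere says that unconnected attempts are not AEs. Where the protocol means causation it says so plainly, as in I.4.e, so its looser wording here may only mean around the time of treatment. Suicides and serious attempts are covered several times over, and the medical monitor and the CHRT provide oversight. H.2.b (exclusion 11) also removes patients judged at significant risk of suicidal behavior.

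Most of this stands, and it rules out three stronger readings that a reader might draw:

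- *That suicide and attempted suicide are AEs only if caused by the IP.* The sentence contains no such restriction, and a causal meaning is one reading among two.
- *That an attempt put down to lack of effect is unrelated by rule and therefore not an AE at all.* I.4.e governs how causality is rated. It does not mention attempts and sets no condition for entry, and I.4.b points the other way.
- *That the loss can be sized by assuming a per-patient risk and computing the chance of at least one event among 52 patients.* The documents give no rate. Such a figure would count every suicide and attempt, including those the SAE rules capture, and would not measure events lost from the AE record.

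It is also fair that one event among 26 per arm could not establish a difference between arms. The issue is a complete and consistent record, not a lost test.

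The reply does not remove the conflict. The timing reading it prefers still disagrees with I.4.b.1, and a general rule does not clearly override the one section dedicated to these events.

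**Conclusion.** The conflict is real and its consequence is limited. The qualifier in I.4.b.4 is undefined and disagrees with I.4.a and I.4.b if causal, or with I.4.b.1 if temporal. The practical exposure is a non-serious attempt that a site judges unconnected with the IP and does not enter as an AE. It could then be absent from the treatment-emergent AE comparison, or be recorded at one site and not at another. Completed suicides, serious attempts and immediate safety oversight are not affected.

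The conclusion rests on the text alone. It assumes that some sites would follow the specific section over the general rule, and that reporting an event to the monitor does not by itself create an AE entry. The Manual of Operations, which is not among the documents, might settle either point. How often such events would occur cannot be estimated from the documents.

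**What to change.** 1. In I.4.b.4, in the words "but occurring in connection with the use of IP, should be reported as AEs", delete everything up to and including the comma. Every suicide and attempted suicide from consent onward is then recorded as an AE under I.4.b and I.4.b.1. Relationship stays in its own field under I.4.b.3 and I.4.e.
2. In the sentence on attempts that are not SAEs, state that the event is entered as an AE in the eCRF as well as being reportable.
3. Reconcile I.4.b.3 and I.4.h with this, by stating that the disease-progression exclusion does not apply to suicide or attempted suicide. Without this step the first change leaves that route open.

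The cost is one phrase deleted and two short clarifications, with matching text in the site guidance. No visit, assessment or analysis is added.
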